- c. If none of the actions (i.e., escalation, de-escalation or elimination) is triggered, we treat the new patients at the current dose.
- d. If the current dose is the lowest dose and the rule indicates dose de-escalation, treat the new patients at the lowest dose unless the number of DLTs reaches the elimination boundary, at which point terminate the trial for safety.
- e. If the current dose is the highest dose and the rule indicates dose escalation, treat the new patients at the highest dose.

3. Repeat step 2 until the maximum sample size (i.e., 40 for Part A or 18 for Part B) is reached or stop the trial if the maximum number of patients treated at the current dose reaches (i.e., 15 for Part A or 12 for Part B).

Figure 6-1 Flowchart for study conduct using the BOIN design

$$* \text{DLT rate} = \frac{\text{Total number of patients who experienced DLT at the current dose}}{\text{Total number of patients treated at the current dose}}$$

Table 6-5 Dose escalation/de-escalation rule for the BOIN Design

Number of patients treated at the current dose ^a	3 ^a	4 ^a	5 ^a	6 ^a	7 ^a	8 ^a	9 ^a	10 ^a	11 ^a	12 ^a	13 ^a	14 ^a	15 ^a
Escalate if # of DLT <=^a	0 ^a	0 ^a	1 ^a	1 ^a	1 ^a	1 ^a	2 ^a	2 ^a	2 ^a	2 ^a	3 ^a	3 ^a	3 ^a
Stay if # of DLT =^a	1 ^a	1 ^a	NA ^a	2 ^a	2 ^a	2 ^a	3 ^a	3 ^a	3 ^a	3/4 ^a	4 ^a	4/5 ^a	4/5 ^a
Deescalate if # of DLT >=^a	2 ^a	2 ^a	2 ^a	3 ^a	3 ^a	3 ^a	4 ^a	4 ^a	4 ^a	5 ^a	5 ^a	6 ^a	6 ^a
Eliminate if # of DLT >=^a	3 ^a	3 ^a	4 ^a	4 ^a	5 ^a	5 ^a	6 ^a	6 ^a	7 ^a	7 ^a	8 ^a	8 ^a	8 ^a

Dose expansion stage:

In order to further explore the safety, pharmacokinetics and efficacy during dose-escalation, dose expansion cohorts will be added in Phase I stage of the study. We plan to recruit up to 15 patients per cohort.

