6.2.4 Definitions of dose limiting toxicities (DLTs)

DLT is defined as: any toxicity meeting the specified criteria and considered at least possibly related to HH2710 (i.e., any toxicity for which a clear alternative etiology such as disease

progression has not been identified) should be considered a DLT per National Cancer Institute Common Terminology Criteria for Adverse events (NCI-CTCAE V5.0) standard, which met any of the following, NCI-CTCAE V5.0 will be used for all grading, and compliance of 80% (i.e. 17 of 21 days) in Cycle 1 is required for a patient to be included in the DLT evaluation. For the purpose of dose-escalation decisions, DLTs will be considered and included in the BOIN. The criteria for defining dose-limiting toxicities see Table 6-6.

Table 6-6 Criteria for defining dose-limiting toxicities

TOXICITY	DLT CRITERIA
Blood and lymphatic system disorders	
≥ Grade 4 hematologic toxicity
 
Grade 3 thrombocytopenia with bleeding or with requirement of transfusion of platelets
 
Any grade febrile neutropenia
 
Note: Given the high frequency of events related to underlying disease in subjects of LCH, the investigator should confirm the causality of these events before judgement of DLTs, based on severity or duration is longer than that expected with standard-of-care treatment or other clinical evidence

Cardiac disorders	
Asymptomatic decrease of LVEF > 10% compared to baseline and the LVEF is below the institution's LLN b.
 
Left ventricular systolic dysfunction CTCAE Grade ≥ 3
 
Other cardiac disorders CTCAE Grade ≥ 3

Vascular disorders Hypertension	Persistent hypertension CTCAE Grade ≥ 3 requiring more than one drug or more intensive therapy than previously administered.
General disorders and administration site conditions	Fatigue CTCAE Grade 3 for > 72 hours
Skin and subcutaneous tissue disorders: Rash and/or photosensitivity	Rash/photosensitivity CTCAE Grade 3 for > 72 hours despite skin toxicity treatment, photosensitivity Grade 4
Eye disorders	Any grade of retinal vein occlusion (RVO)
Gastrointestinal disorders	
Diarrhea CTCAE Grade 3 > 72 hrs., despite the use of anti-diarrhea therapy; Diarrhea Grade 4
 
Nausea/ vomiting CTCAE Grade 3 > 72 hrs., despite the use of anti-emetic therapy; Vomiting Grade 4

TOXICITY	DLT CRITERIA
	Pancreatitis CTCAE Grade ≥ 3
Investigations ^a	
	Blood bilirubin CTCAE Grade ≥ 3

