	ALT/AST > 3 ULN and concomitant TBL > 2 ULN in the absence of evidence of biliary obstruction (i.e., significant elevation of ALP) or some other explanation of the injury (e.g., viral hepatitis, alcohol hepatitis) of any duration (i.e. Hy's law)
	AST or ALT CTCAE Grade 3 for > 72 hours
	AST or ALT CTCAE Grade 4
	Serum alkaline phosphatase CTCAE Grade 3
	Serum lipase and/or serum amylase (asymptomatic) CTCAE Grade 3 > 72 hours
	Serum lipase and/or serum amylase CTCAE Grade 4
	Serum creatinine CTCAE Grade ≥ 3
	Serum CK/CPK CTCAE Grade 3 for > 72 hours
	Serum CK/CPK CTCAE Grade 4
	Neutrophil count CTCAE Grade 3 for > 72 hours
	Neutrophil count CTCAE Grade 4
	Platelet count CTCAE Grade 3 with signs of bleeding
	Platelet count CTCAE Grade 4
	ECG QTc interval prolonged CTCAE \geq Grade 3
	Electrolyte imbalance Grade 4; Asymptomatic electrolyte imbalance Grade 3 > 72 hours
Other hematologic & non-hematologic toxicities	Any other CTCAE Grade ≥ 3 toxicity except: Lymphocyte count decreased (lymphopenia) CTCAE Grade ≥ 3 unless clinically significant
	Other clinically significant/unacceptable toxic events not listed, judged by the SMC as DLT;

TOXICITY	DLT CRITERIA
All AEs of the specified grade and toxicity must be considered a DLT if they cannot definitively be attributed to disease progression or other extraneous cause.	

^a For any CTCAE Grade 3 or 4 hepatic toxicity that does not resolve within 7 days to CTCAE Grade ≤ 1 (or CTCAE Grade ≤ 2 if liver infiltration with tumor present), an abdominal CT scan must be performed to assess if it is related to disease progression.
	

CTCAE V5.0 will be used for all grading.
	

Patients may receive supportive care (e.g. Packed red blood cells) as per local institutional guidelines.
	

G-CSF may be used to treat patients who have developed dose-limiting neutropenia, as per institutional guidelines, following discontinuation of HH2710 treatment. Optimal therapy for vomiting or diarrhea will be based in institutional guidelines, with consideration of the prohibited medications listed in this protocol. Grade 3 laboratory investigations other than serum creatinine, bilirubin, AST or ALT will not be considered a DLT unless they are associated with clinical manifestations and judged by the SMC.
	

For the exceptions provided, the Grade 3 AEs should resolve to \leq Grade 1 within 72 hours
	

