6.3 Dose modifications

6.3.1 Dose modification and dose delay

For patients who do not tolerate the protocol-specified dosing schedule, dose adjustments are permitted in order to allow the patient to continue the study treatment. The following guidelines need to be applied:

These changes must be recorded on the Dosage Administration Record CRF.

All dose modifications should be based on the worst preceding toxicity.

Each patient is only allowed 2 dose reductions as showed in [Table 6-7](#).

If a patient requires a dose interruption of > 14 days from the intended day of the next scheduled dose, then the patient must be discontinued from the study. Patients who discontinue the study for a study related adverse event or an abnormal laboratory value must be followed as described in [Table 6-](#).

Table 6-7 Dose adjustment of HH2710

	HH2710(mg)
Dose	Starting Dose
First dose reduction	75% of the starting dose*
Second dose reduction	50% of the starting dose*

* The actual reduced dose should take into account the drug specification

Adjust reference values in the table below according to the CTCAE V5.0 used in the study.

The criteria for interruption and re-initiation of HH2710 treatment is showed in [Table 6-](#)

Table 6-8 Criteria for interruption, re-initiation of HH2710 treatment and permanently discontinuation

Recommended dose modifications for HH2710	
Worst toxicity	Recommended dose modifications any time during a cycle of therapy, including intended day of dosing^b
CTCAE Grade^a (value)	
No toxicity	Maintain dose level
Investigations (Hematologic)	
Neutropenia (ANC)	
Grade 1 (ANC < LLN - 1500/mm ³)	Maintain dose level
Grade 2 (ANC < 1500 - 1000/mm ³)	Maintain dose level
Grade 3 (ANC < 1000 - 500/mm ³)	Discontinue HH2710: 
 - If elevation lasts for \leq 7 days: Resume treatment at same dose level - If elevation lasts for >7 days: Resume treatment at ≥ 1 dose level
Grade 4 (ANC < 500/mm ³)	Discontinue dose until resolved to \leq Grade 2, then ≥ 1 dose level 
If there is no recovery to \leq Grade 2 or there is recurrent grade 3 or 4 neutropenia, G-CSF/Neulasta may be given at physician discretion.
 
If no recovery to \leq Grade 2, permanently discontinue HH2710

Thrombocytopenia	
Grade 1 (PLT < LLN - 75,000/mm ³)	Maintain dose level
Grade 2 (PLT < 75,000 - 50,000/mm ³)	Maintain dose level

Recommended dose modifications for HH2710	

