Grade 1 (>ULN - 1.5 x ULN if baseline was normal; > 1.0 - 1.5 x baseline if baseline was abnormal)	Maintain dose level

Recommended dose modifications for HH2710	
Worst toxicity CTCAE Grade^a (value)	Recommended dose modifications any time during a cycle of therapy, including intended day of dosing^b
Grade 2 (>1.5 - 3.0 x ULN if baseline was normal; >1.5 - 3.0 x baseline if baseline was abnormal)	Discontinue dose until resolved to \leq Grade 1, then: 
 - If resolved in \leq 7 days, then maintain dose level - If resolved in > 7 days, then \downarrow 1 dose level
Grade 3 (>3.0 - 10.0 x ULN if baseline was normal; >3.0 - 10.0 x baseline if baseline was abnormal)	Discontinue dose until resolved to \leq Grade 1, then: 
 - If resolved in \leq 7 days, then \downarrow 1 dose level - If resolved in > 7 days, then discontinue patient from study drug treatment
Grade 4 (>10.0 x ULN if baseline was normal; >10.0 x baseline if baseline was abnormal)	Permanently discontinue HH2710
AST or ALT	
Grade 1 (>ULN - 3.0 x ULN if baseline was normal; 1.5 - 3.0 x baseline if baseline was abnormal)	Maintain dose level
Grade 2 (>3.0 - 5.0 x ULN if baseline was normal; >3.0 - 5.0 x baseline if baseline was abnormal)	Maintain dose level
Grade 3 (>5.0 - 20.0 x ULN if baseline was normal; >5.0 - 20.0 x baseline if baseline was abnormal)	Discontinue dose until resolved to \leq Grade 1 (or \leq Grade 2 if liver metastases present), then: 
 - If resolved in \leq 7 days, then maintain dose level - If resolved in > 7 days, then \downarrow 1 dose level
Grade 4 (>20.0 x ULN if baseline was normal; >20.0 x baseline if baseline was abnormal)	Permanently discontinue HH2710

Recommended dose modifications for HH2710	
Worst toxicity CTCAE Grade^a (value)	Recommended dose modifications any time during a cycle of therapy, including intended day of dosing^b
ALT/AST > 3 ULN and concomitant TBL > 2 ULN in the absence of evidence of biliary obstruction (i.e., significant elevation of ALP) or some other explanation of the injury (e.g., viral hepatitis, alcohol hepatitis) of any duration (i.e. Hy's law)	Permanently discontinue HH2710
Investigation (metabolic)**	
amylase and/or lipase elevation	
Grade 1 (> ULN - 1.5 x ULN)	Maintain dose level
Grade 2 (>1.5-2.0xULN; >2.0-5.0xULN and asymptomatic)	Maintain dose level

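### The DLT rate has two conflicting denominators: patients with 17 of 21 dosed days, with no exception for a DLT (Section 6.2.4), or everyone treated (Figure 6-1, Table 6-5)

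*Protocol*

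**What the plan says.** - **Protocol 6.2.4, opening text:** "compliance of 80% (i.e. 17 of 21 days) in Cycle 1 is required for a patient to be included in the DLT evaluation". The next sentence reads "For the purpose of dose-escalation decisions, DLTs will be considered and included in the BOIN". Neither mentions a patient who has a DLT and falls short of 17 days.
- **Protocol Figure 6-1 and Table 6-5 (Section 6.2.3):** the DLT rate is divided by "Total number of patients treated at the current dose", and the columns of Table 6-5 are indexed the same way.
- **Protocol Table 6-6:** "AST or ALT CTCAE Grade 3 for > 72 hours" is a DLT. The note to the table says "All AEs of the specified grade and toxicity must be considered a DLT" unless progression or another outside cause definitely explains them.
- **Protocol 6.3.1 and Table 6-8:** for Grade 3 AST or ALT, drug is stopped until recovery. The branch beginning "If resolved in > 7 days, then" allows treatment to resume one dose level lower. Only a patient who "requires a dose interruption of > 14 days from the intended day of the next scheduled dose" must be discontinued.
- **Protocol 7.1.4.3:** withdrawn patients are replaced, except those who left for an intolerable drug-related AE in the DLT window. The same section also says that patients are not replaced, and it allows a new patient for a non-evaluable subject. It does not define evaluable.
- **SAP Section 6 and 8.8.1.2:** there is no DLT-evaluable set, and the only planned DLT output is a listing. SAP 3.1.1 keeps the isotonic MTD estimate, and SAP 7.2 bases the RP2D partly on observed DLTs.

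**The concern.** Section 6.2.4 and Figure 6-1 give different rules for who enters the same rate, and neither is right alone.

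The 17-day rule properly removes patients who had too little drug to be called DLT-free. Read literally, it also removes a patient whose DLT led to the hold. The all-treated rule keeps every DLT, but it counts a patient who left early without one as a complete non-event. Both errors push the rate down, which favours escalation.

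The open case is a DLT patient held for 5 to 14 days who stays in the study. A longer hold leads to discontinuation, and withdrawal for an intolerable drug-related AE falls under the no-replacement clause. The protocol provides for such a case in its own handling of Grade 3 AST or ALT. It does not say whether a hold that it requires counts as failed compliance.

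This rate drives each BOIN decision and the isotonic estimate of the MTD.

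**Working it through.** **1. The plan's own boundaries.** The target is φ = 0.30 (Section 6.2.3). I assume the usual defaults φ₁ = 0.6φ = 0.18 and φ₂ = 1.4φ = 0.42, which the protocol does not state.

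- λₑ = ln[(1−φ₁)/(1−φ)] / ln[φ(1−φ₁)/(φ₁(1−φ))] = 0.2365
- λ_d = ln[(1−φ)/(1−φ₂)] / ln[φ₂(1−φ)/(φ(1−φ₂))] = 0.3585

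These agree with the stated 0.236 and 0.359. Taking floor(nλₑ) and ceil(nλ_d) for n = 3 to 15 reproduces all 26 entries of the escalate and de-escalate rows of Table 6-5. The boundaries are sound; the question is which counts go into them.

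**2. When a hold takes a patient below 17 days.** 80% of 21 is 16.8, hence 17, so at most 4 days may be missed. With onset on day d and a hold of h days, dosed days = 21 − min(h, 21−d). This is below 17 only if h ≥ 5 and d ≤ 16. For holds of 8 to 14 days with d ≤ 16, dosed days run from 7 to 16. If onset is uniform over days 1 to 21, 16/21 (76%) of holds of 5 to 14 days leave the patient short.

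**3. Decisions that flip under Table 6-5.**

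- Two DLTs in 3 patients means de-escalate. If both DLT patients fall below 17 days and are substituted by patients without a DLT, 0 of 3 means escalate.
- One DLT in 3 evaluable patients means stay. Add two early leavers without a DLT, and 1 of 5 means escalate.

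**4. Literal 17-day rule.** Let s be the share of all DLT patients held 5 to 14 days and not withdrawn. The documents give neither s nor onset times, so these are assumptions. Patients below 17 days are taken as non-evaluable and substituted; DLT patients who withdraw are counted. With true rate p and f = (16/21)s:

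- apparent rate q = p(1−f)/(1−pf)
- P(escalate by 6) = (1−q)³ + 3q(1−q)²·(1−q)³, from escalation at 0 of 3 or at most 1 of 6

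| p | s | f | q | P(escalate by 6) |
|---|---|---|---|---|
| 0.40 | 0 | 0 | 0.400 | 0.309 |
| 0.40 | 0.25 | 0.190 | 0.351 | 0.395 |
| 0.40 | 0.50 | 0.381 | 0.292 | 0.510 |
| 0.30 | 0 | 0 | 0.300 | 0.494 |
| 0.30 | 0.25 | 0.190 | 0.258 | 0.584 |
| 0.30 | 0.50 | 0.381 | 0.210 | 0.688 |

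If every onset falls by day 16 (f = s), p = 0.40 gives q = 0.333 and 0.428 at s = 0.25, and q = 0.250 and 0.600 at s = 0.50. The apparent rate reaches 0.359 at f = (0.400−0.359)/(0.400×0.641) = 0.160, that is s = 0.160×21/16 = 0.21.

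**5. All-treated rule.** Let w be the share of treated patients who fall below 17 days without a DLT, again an assumption. Suppose none shows a DLT before leaving, which makes the effect an upper bound. Then q = p(1−w). At p = 0.40:

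- w = 0.1: q = 0.36, P(escalate by 6) = 0.378
- w = 0.2: q = 0.32, P(escalate by 6) = 0.454

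**The case against.** The strongest reply is that no one would in practice drop a DLT patient. The sentence after the compliance clause puts DLTs into the BOIN, the note to Table 6-6 says that qualifying events must be treated as DLTs, and Section 7.1.4.3 protects DLT withdrawals from replacement. A specific inclusion rule can also be read as qualifying the generic formula in Figure 6-1. The one DLT reported so far, at 800 mg, is given as 1 of 4 with 4 enrolled, so it was counted.

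This shows intent, and it stands as such. It does not settle the rule. None of these texts says that a DLT patient below 17 days is evaluable, and the no-replacement clause does not cover a patient who is held but stays in the study. The dosed days of the 800 mg patient are not given. If the specific rule does govern, its missing exception matters more.

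Three further points stand:

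- If a required hold is not failed compliance, the exclusion effect is nil (the s = 0 rows).
- The values of s and w have no source in the documents. Substitution is discretionary, and replacing early leavers, if it removes them from the count, would reduce the all-treated effect.
- Table 6-5 does not decide alone. Non-DLT toxicity is reviewed (6.2.3.1), as are Grade 2 or higher AEs for all patients at the dose, and the SMC uses all PK and safety data (6.2.4). SAP Section 7 says that the program has stopped and that many analyses may not be run.

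**Conclusion.** The concern holds. The two rules cannot both govern one rate, and each, followed as written, can understate it. The direction and the possible decision flips follow from the documents. The size does not: at a true rate of 40%, the rise in P(escalate by 6) from 0.31 to 0.40–0.51 assumes s of 0.25 to 0.50, uniform onset and substitution; the rise to 0.38–0.45 assumes w of 0.1 to 0.2 and is an upper bound.

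The consequence for patients is limited by the safety reviews and by the stop of the program. What remains is that the DLT rates to be reported, and any MTD estimate built on them, have no single stated denominator. This should be fixed. Confidence is medium because the size rests on assumed inputs.

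**What to change.** Reconcile Section 6.2.4, Figure 6-1 with Table 6-5, and Section 7.1.4.3 through one DLT-evaluable set: patients with at least one dose who either had a DLT in Cycle 1, whatever the number of days dosed, or completed the 21-day window with at least 80% compliance and no DLT. State that only patients without a DLT can be non-evaluable and topped up, and say how a required hold counts towards compliance. Use the set for both numerator and denominator in Figure 6-1, Table 6-5 and the isotonic estimate.

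In the SAP, add the set to Section 6 and report DLT counts and rates by dose on it, next to the planned listing.

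The cost is a sentence or two in 6.2.4, one in 7.1.4.3, a matching definition under Figure 6-1, one analysis set and one small table. No extra patients or procedures are needed, and no dose or clinical rule changes. With the program stopped, the SAP set and table are the parts that still matter.

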6.3 Dose modifications

6.3.1 Dose modification and dose delay

For patients who do not tolerate the protocol-specified dosing schedule, dose adjustments are permitted in order to allow the patient to continue the study treatment. The following guidelines need to be applied:

These changes must be recorded on the Dosage Administration Record CRF.

All dose modifications should be based on the worst preceding toxicity.

Each patient is only allowed 2 dose reductions as showed in [Table 6-7](#).

If a patient requires a dose interruption of > 14 days from the intended day of the next scheduled dose, then the patient must be discontinued from the study. Patients who discontinue the study for a study related adverse event or an abnormal laboratory value must be followed as described in [Table 6-](#).

Table 6-7 Dose adjustment of HH2710

	HH2710(mg)
Dose	Starting Dose
First dose reduction	75% of the starting dose*
Second dose reduction	50% of the starting dose*

* The actual reduced dose should take into account the drug specification

Adjust reference values in the table below according to the CTCAE V5.0 used in the study.

The criteria for interruption and re-initiation of HH2710 treatment is showed in [Table 6-](#)

Table 6-8 Criteria for interruption, re-initiation of HH2710 treatment and permanently discontinuation

Recommended dose modifications for HH2710	
Worst toxicity	Recommended dose modifications any time during a cycle of therapy, including intended day of dosing^b
CTCAE Grade^a (value)	
No toxicity	Maintain dose level
Investigations (Hematologic)	
Neutropenia (ANC)	
Grade 1 (ANC < LLN - 1500/mm ³)	Maintain dose level
Grade 2 (ANC < 1500 - 1000/mm ³)	Maintain dose level
Grade 3 (ANC < 1000 - 500/mm ³)	Discontinue HH2710: 
 - If elevation lasts for \leq 7 days: Resume treatment at same dose level - If elevation lasts for >7 days: Resume treatment at ≥ 1 dose level
Grade 4 (ANC < 500/mm ³)	Discontinue dose until resolved to \leq Grade 2, then ≥ 1 dose level 
If there is no recovery to \leq Grade 2 or there is recurrent grade 3 or 4 neutropenia, G-CSF/Neulasta may be given at physician discretion.
 
If no recovery to \leq Grade 2, permanently discontinue HH2710

Thrombocytopenia	
Grade 1 (PLT < LLN - 75,000/mm ³)	Maintain dose level
Grade 2 (PLT < 75,000 - 50,000/mm ³)	Maintain dose level

Recommended dose modifications for HH2710	
Worst toxicity CTCAE Grade^a (value)	Recommended dose modifications any time during a cycle of therapy, including intended day of dosing^b
Grade 3 (PLT < 50,000 - 25,000/mm ³)	
Discontinue dose until resolved to \leq Grade 2, then:
 
 - If resolved in \leq 7 days, then maintain dose level - If resolved in $>$ 7 days, then \downarrow 1 dose level 
If no recovery to \leq Grade 2, permanently discontinue HH2710
 
Second occurrence: discontinue until toxicity resolves to \leq Grade 2, reduce to by another dose level.
 
3rd occurrence permanently discontinue HH2710.

Grade 4 (PLT < 25,000/mm ³)	
Discontinue dose until resolved to \leq Grade 2, then \downarrow 1 dose level
 
If no recovery to \leq Grade 2, permanently discontinue HH2710
 
Second occurrence: discontinue until toxicity resolves to \leq Grade 2, reduce to by another dose level.
 
3rd occurrence permanently discontinue HH2710.

Febrile neutropenia (ANC < 1.0 x 10 ⁹ /L, fever \geq 38.5°C)	Discontinue dose until resolved, then \downarrow 1 dose level
First episode	
Discontinue HH2710 until afebrile and ANC $>$ 1000.
 
Add Filgrastim/Neulasta per physician discretion.

Second episode	
Discontinue HH2710 until afebrile and ANC $>$ 1000.
 
Add Filgrastim/ Neulasta per treating physician discretion.
 
Restart HH2710 at dose reduced by one dose level and monitor as clinically.

Recommended dose modifications for HH2710	
Worst toxicity CTCAE Grade^a (value)	Recommended dose modifications any time during a cycle of therapy, including intended day of dosing^b
Third episode	Discontinue HH2710 until afebrile and ANC >1000. Add Filgrastim/ Neulasta per treating physician discretion. Restart HH2710 reduced by another dose level and monitor as clinically indicated.
Fourth episode	Permanently discontinue HH2710 and continue follow-up protocol.
Investigations (Hematologic) for LCH	Manage as per institutional standard or global guidance.
Investigations (Renal)	
Serum creatinine	
Grade 1 (> ULN - 1.5 x ULN)	Maintain dose level
Grade 2 (>1.5 - 3.0 x baseline; > 1.5 - 3.0 x ULN)	Discontinue dose until resolved to \leq Grade 1 or baseline, then maintain dose level
Grade 3 (>3.0 x baseline; > 3.0 - 6.0 x ULN)	Permanently discontinue HH2710
Grade 4 (> 6.0 x ULN)	Permanently discontinue HH2710
Investigations (Hepatic)*	
Bilirubin	
Grade 1 (>ULN - 1.5 x ULN if baseline was normal; > 1.0 - 1.5 x baseline if baseline was abnormal)	Maintain dose level

Recommended dose modifications for HH2710	
Worst toxicity CTCAE Grade^a (value)	Recommended dose modifications any time during a cycle of therapy, including intended day of dosing^b
Grade 2 (>1.5 - 3.0 x ULN if baseline was normal; >1.5 - 3.0 x baseline if baseline was abnormal)	Discontinue dose until resolved to \leq Grade 1, then: 
 - If resolved in \leq 7 days, then maintain dose level - If resolved in > 7 days, then \downarrow 1 dose level
Grade 3 (>3.0 - 10.0 x ULN if baseline was normal; >3.0 - 10.0 x baseline if baseline was abnormal)	Discontinue dose until resolved to \leq Grade 1, then: 
 - If resolved in \leq 7 days, then \downarrow 1 dose level - If resolved in > 7 days, then discontinue patient from study drug treatment
Grade 4 (>10.0 x ULN if baseline was normal; >10.0 x baseline if baseline was abnormal)	Permanently discontinue HH2710
AST or ALT	
Grade 1 (>ULN - 3.0 x ULN if baseline was normal; 1.5 - 3.0 x baseline if baseline was abnormal)	Maintain dose level
Grade 2 (>3.0 - 5.0 x ULN if baseline was normal; >3.0 - 5.0 x baseline if baseline was abnormal)	Maintain dose level
Grade 3 (>5.0 - 20.0 x ULN if baseline was normal; >5.0 - 20.0 x baseline if baseline was abnormal)	Discontinue dose until resolved to \leq Grade 1 (or \leq Grade 2 if liver metastases present), then: 
 - If resolved in \leq 7 days, then maintain dose level - If resolved in > 7 days, then \downarrow 1 dose level
Grade 4 (>20.0 x ULN if baseline was normal; >20.0 x baseline if baseline was abnormal)	Permanently discontinue HH2710

Recommended dose modifications for HH2710	
Worst toxicity CTCAE Grade^a (value)	Recommended dose modifications any time during a cycle of therapy, including intended day of dosing^b
ALT/AST > 3 ULN and concomitant TBL > 2 ULN in the absence of evidence of biliary obstruction (i.e., significant elevation of ALP) or some other explanation of the injury (e.g., viral hepatitis, alcohol hepatitis) of any duration (i.e. Hy's law)	Permanently discontinue HH2710
Investigation (metabolic)**	
amylase and/or lipase elevation	
Grade 1 (> ULN - 1.5 x ULN)	Maintain dose level
Grade 2 (>1.5-2.0xULN; >2.0-5.0xULN and asymptomatic)	Maintain dose level
Grade 3 (>2.0 - 5.0 x ULN with signs or symptoms; >5.0 x ULN and asymptomatic)	Discontinue dose of until resolved to Grade \leq 2, then: 
 - If resolved in \leq 7 days, then maintain dose level - If resolved in > 7 days, then \downarrow 1 dose level
Grade 4 (>5.0 x ULN and with signs or symptoms)	Permanently discontinue HH2710.
Cardiac general	
Grade 1 or 2	Maintain dose level
Grade 3	Discontinue dose until resolved to \leq Grade 1, then \downarrow 1 dose level
Grade 4	Discontinue dose and discontinue patient from study drug treatment

Recommended dose modifications for HH2710	
Worst toxicity CTCAE Grade^a (value)	Recommended dose modifications any time during a cycle of therapy, including intended day of dosing^b
Electrocardiogram QT corrected (QTc) interval prolonged	
Grade 1 or 2 Heart Failure	Maintain dose level
Grade 3 Heart Failure	Permanently discontinue HH2710 and discontinue patient from study drug treatment
Grade 4 Heart Failure	Permanently discontinue HH2710 and discontinue patient from study drug treatment
Grade 2 Ejection Fraction (EF) Decreased (resting EF: 50-40%; or 10-19% drop from baseline)	Discontinue HH2710 until ejection fraction returns to a value greater than the institutional lower limit of normal and the absolute decrease from baseline is $\leq 15\%$, then maintain dose level.
Grade 3-4 EF Decreased (resting EF 39-20%; or $\geq 20\%$ drop from baseline)	Permanently discontinue HH2710
Grade 1 and 2 (QTcF 450-500ms)	Maintain dose level
Grade 3 (QTcF ≥ 501 ms on at least two separate ECGs)	Discontinue dose until resolved to Grade ≤ 2 , then: 
 - If resolved in ≤ 7 days, then maintain dose level - If resolved in > 7 days, then $\downarrow 1$ dose level
Grade 4 (QTcF ≥ 501 ms or > 60 ms change from baseline and Torsades de pointes or polymorphic ventricular tachycardia or signs/symptoms of serious)	Permanently discontinue HH2710
Eye disorders	
Retinal vein occlusion (RVO)	Permanently discontinue HH2710.

Recommended dose modifications for HH2710	
Worst toxicity CTCAE Grade^a (value)	Recommended dose modifications any time during a cycle of therapy, including intended day of dosing^b
Other Grade 1 or 2 eye AEs	Discontinue dose until resolved to baseline, HH2710 could be restarted after assessed by ophthalmologist and investigator, maintain dose level or one dose level reduced as clinically indicated.
≥ Grade 3 ocular/vision symptoms interfering with ADL (Activities of daily living) or requiring medical intervention	Permanently discontinue HH2710.
Vascular disorders	
Hypertension	
Grade 1 and 2	Maintain dose level
Grade 3	Discontinue dose until resolved ≤ Grade 1, then ↓ 1 dose level
Grade 4	Permanently discontinue HH2710
Gastrointestinal	
Pancreatitis	
Grade 2	Maintain dose level
Grade ≥ 3	Permanently discontinue HH2710
Diarrhea***	
Grade 1 and 2	Maintain dose level, but initiate anti-diarrhea therapy

Recommended dose modifications for HH2710	
Worst toxicity CTCAE Grade^a (value)	Recommended dose modifications any time during a cycle of therapy, including intended day of dosing^b
Grade 3	Discontinue dose until resolved to \leq grade 1, then \downarrow 1 dose level
Grade 4	Permanently discontinue HH2710
Skin and subcutaneous tissue disorders	
Rash/photosensitivity	
Grade 1 and 2	Maintain dose level. Consider to initiate institute appropriate skin toxicity therapy (such as antihistamines, topical corticosteroids and low-dose systemic corticosteroids)
Grade 3, despite skin toxicity therapy	Discontinue dose until resolved to Grade \leq 1, then: 
 – If resolved in \leq 7 days, then \downarrow 1 dose level – If resolved in $>$ 7 days, then discontinue HH2710
Grade 4, despite skin toxicity therapy	Permanently discontinue HH2710
General disorders and administration site conditions	
Fatigue/ Asthenia	
Grade 1 or 2	Maintain dose level
Grade 3	Discontinue dose until resolved to \leq grade 1, then: 
 – If resolved in \leq 7 days, then maintain dose level – If resolved in $>$ 7 days, then \downarrow if resolved in
Other adverse events****	

Recommended dose modifications for HH2710	
Worst toxicity CTCAE Grade^a (value)	Recommended dose modifications any time during a cycle of therapy, including intended day of dosing^b
Grade 1 or 2	Maintain dose level
Grade 3	Discontinue dose until resolved to \leq grade 1, then \downarrow 1 dose level
Grade 4	Permanently discontinue HH2710 Discontinue dose for \geq grade 3 vomiting or grade 3 nausea only if the vomiting or nausea cannot be controlled with optimal antiemetic (as per local practice)

All dose modifications should be based on the worst preceding toxicity.

^a Common Toxicity Criteria for Adverse Events (CTCAE V5.0)

^b If the investigator considers it to be at patient's best interest to resume therapy before the toxicity has resolved to Grade 1 or 2 mentioned above, this may be permitted on a case by case basis, following discussion with Haihe.

* Note: If Grade 3 or 4 hyper-bilirubinemia is due to the indirect (non-conjugated) component only, and hemolysis as the etiology has been ruled out as per institutional guidelines (e.g., review of peripheral blood smear and haptoglobin determination), then \downarrow 1 dose level* and continue treatment at the discretion of the investigator.

**Note: A CT scan or other imaging study to assess the pancreas, liver, and gallbladder must be performed within 1 week of the first occurrence of any \geq Grade 3 of amylase and/or lipase. If asymptomatic Grade 2 elevations of lipase and/or amylase occur again at the reduced dose, patients will be discontinued permanently from study treatment.

***Note: antidiarrheal medication is recommended at the first sign of abdominal cramping, loose stools or overt diarrhea

****Note: This is a general guidance for the other AEs except the above mentioned, and it is recommended that the specialists were involved for special case, and AE must be under adequate treatment before discontinuing.

